### Sensitivity Analysis

A sensitivity analysis will be performed including any additional information gathered between the last study treatment administration and Visit 9 (follow-up period), therefore this analysis will include all data collected from the first treatment administration to the date of study completion or withdrawal. The need for mechanical ventilation is not captured during the follow-up period however the start time of any mechanical ventilation is captured. Therefore, the sensitivity analysis will consider a subject to need mechanical ventilation during the study if any of the following are recorded from the date and time of first study treatment administration to the date of study completion/withdrawal:

- withdrawal from treatment with the reason for withdrawal recorded as need for mechanical invasive or non-invasive ventilation,
- any entry on the Mechanical Ventilation eCRF page indicating that ventilation was required,
- death as recorded on the adverse event or withdrawal from study pages.

The logistic regression model described above will be repeated.

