## Sensitivity Analysis

The analysis will be repeated to include subjects who record the need for mechanical ventilation or death between the last study treatment administration and Visit 9 (follow-up period), therefore this analysis will include all data collected from the first treatment administration to the date of study completion or withdrawal to further support the results of the study. For subjects who do not record the need for mechanical ventilation or death during the treatment period, but do record one or both of these during the follow-up period, the earliest of the following will be used to calculate the time to need of ventilation: start time and date as entered on the mechanical ventilation eCRF page or time and date of death as entered on the adverse events page. For subjects who do not record a need for ventilation and who do not die at any point following first study treatment administration, the time to need of ventilation will be right censored at the date of withdrawal from study or study completion.

It should be noted that the decision time is used for subjects who record withdrawal due to mechanical ventilation but the start time of mechanical ventilation will be used for subjects who do not withdraw due to mechanical ventilation but do record an entry on the mechanical ventilation eCRF page.

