	12) Male subjects not willing to use contraceptive methods as described in Section 5.3.1								
	13) Subjects known or suspected of not being able to comply with this trial protocol (e.g. due to alcoholism, drug dependency or psychological disorder)								
	due to dicononism, drug dependency of psychological disorder)								

Vicore Pharma AB Version: 2.0 Trial ID: VP-C21-006 Date: 14-Aug-2020

A subject will be withdrawn from IMP if any of the following occurs:
Need for mechanical invasive or non-invasive ventilation
Discharge from the hospital/controlled facility
 Major protocol deviations as defined by Sponsor.
• Sponsor decision to stop the trial or to stop the subject's participation in the trial; reasons may include medical, safety, or regulatory issues, or other reasons consistent with applicable laws, regulations, and GCP.
It is the wish of the subject for any reason
The Investigator judges it necessary due to medical reasons
 Adverse events such as: Serious cardiovascular complications such as severe peripheral oedema or significant bradycardia indicating a potential risk for the subject as evaluated by the Investigator Moderate to severe skin rashes as judged by the Investigator e.g. Stevens-Johnson syndrome and toxic epidermal necrolysis
Pregnancy
Withdrawal from trial: • Enrolment in other clinical studies involving investigational products or enrolment in other types of clinical research judged not to be scientifically or medically compatible with this trial.
Disallowed treatment during the trial period
It is the wish of the subject for any reason The description of the subject for any reason of th
 The Investigator judges it necessary due to medical reasons Adverse events
 Adverse events Lost to follow-up
IMP will be delivered as 50 mg capsules packed in plastic container units with 28 capsules in each.
Each unit will contain either C21 or matching placebo.
At the trial site, IMP must be stored separately from normal clinic stocks in a securely locked area only accessible to authorised trial personnel.
Labeling of the IMP will be in local language and done in compliance with GMP Annex 13 (GMP 2003) and local regulatory requirements.
IMP will be administered twice daily to the subjects for 7 days as follows:

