2 FLOW CHARTS

Table 1 Flow Chart for Trial Procedures

	Screening		Treatment Period			With- drawal ¹⁾	End-of- Trial ²⁾			
Visit Number	Visit 1	Visit 2	Visit 3	Visit 4	Visit 5	Visit 6	Visit 7	Visit 8	-	Visit 9
Visit window (days allowed from previous visit)		1-3	1	1	1	1	1	1	-	7-10 ²⁾
Eligibility / General										
Informed consent	X									
Check eligibility criteria	X	x ³⁾								
Demographics	X									
Medical history	X									
Randomisation		X								
Supplemental O ₂	X	X	X	X	X	X	X	X		X
Previous/concomitant medication	x	X	X	x	x	x	x	x	х	x
Check of withdrawal criteria		X	X	x	x	x	x	x		
Clinical Safety										
Physical examination ⁴⁾	x ⁴⁾	X	X	X	X	X	X	X		
Body weight	X									
Height	X									
Body temperature	X	X	X	X	X	X	X	X		
Vital signs	X	X	X	X	X	X	X	X		
12-lead ECG ⁵⁾	X									
Adverse events	X	X	X	X	X	X	X	X	X	х
IMP										
IMP administration ⁶⁾		X	X	x	X	X	X	X		
Check of fasting criteria		X	X	X	X	X	X	X		
Drug accountability								X	X	

- 1) Additional withdrawal assessments must be performed at Visit 2-8 if the subject is prematurely withdrawn from IMP (see Section 6.5.3)
- 2) An end-of-trial visit for all randomised subjects who received IMP must be performed 7-10 days after the last dose of IMP. The end-of-trial visit must also be performed if a subject is withdrawn from the trial for any reason.
- 3) Re-evaluation of in-/exclusion criteria including evaluation of ECG and laboratory results from Visit 1
- 4) A complete physical examination will be performed at Visit 1. At Visits 2-8, only a short physical examination will be performed (see Section 8.2.4)
- 5) All ECGs will be reviewed locally
- 6) IMP is administered twice daily (see Section 7.4)

Vicore Pharma AB Version: 2.0 Trial ID: VP-C21-006 Date: 14-Aug-2020

Table 2 Flow Chart for Laboratory Assessments

Visit	Screening		Treatment Period				With- drawal ¹⁾	End-of- Trial ²⁾		
Visit Number	Visit 1	Visit 2	Visit 3	Visit 4	Visit 5	Visit 6	Visit 7	Visit 8	-	Visit 9
Visit window (days allowed from previous visit)		1-3	1	1	1	1	1	1	-	7-10
Laboratory Sampling										
HCV Ab	X									
HBsAg	X									
HIV 1+2 Ag/Ab	X									
Biochemistry ⁷⁾	X	х	x	X	X	X	X	X		
Haematology ⁸⁾	X	X	X	X	X	X	X	X		
CRP	X	X	X	X	X	X	X	X	X	
IL-6		X	X	X	X	X	X	X		
IL-10		X	X	X	X	X	X	X		
TNF		X	X	X	X	X	X	X		
CA125		X	X	Х	X	X	X	X		
Ferritin		X	X	X	X	X	X	X		
Urinalysis 9)	Х	Х	X	X	X	X	X	X		
Biomarkers		X						X	X	
Pregnancy testing 10) 11)	X							X	X	

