5.4.2 Withdrawal from Trial

- Enrolment in other clinical trials involving investigational products or enrolment in other types of clinical research judged not to be scientifically or medically compatible with this trial.
- Disallowed treatment during the trial period
- It is the wish of the subject for any reason
- The Investigator judges it necessary due to medical reasons
- Adverse events
- Lost to follow-up

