6.5.4 End-of-Trial (Visit 9)

Visit 9 is performed for all randomised subjects 7-10 days after the last IMP administration and may be performed as a telephone contact.

The following procedures are performed:

- Concomitant medication
- Date of discharge
- Use of supplemental O₂
- Use of mechanical invasive and non-invasive mechanical ventilation
- Adverse events

If a subject is prematurely withdrawn from IMP, Visit 9 must be performed 7-10 days after last IMP dose (see Section 5.4.1).

Vicore Pharma AB Version: 2.0 Trial ID: VP-C21-006 Date: 14-Aug-2020

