9.4 Follow-up on Adverse Events

All AEs should be followed until they are resolved or the subject's participation in the trial ends, whichever comes first.

SAEs and severe, non-serious AEs considered related to IMP should be followed on a regular basis according to the investigator's clinical judgment until a final outcome has been established.

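### The two ventilation sensitivity analyses give conflicting ends for follow-up (Visit 9, or study withdrawal), so an event recorded at Visit 9 after trial withdrawal may not count

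*Combined protocol and SAP*

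**What the plan says.** **Leaving the trial.** Protocol Section 1 and Section 5.4.2 list the reasons for withdrawal from the trial. They include "Enrolment in other clinical trials involving investigational products or enrolment in other types of clinical research" (if judged incompatible with this trial), "Disallowed treatment during the trial period", "The Investigator judges it necessary due to medical reasons", and adverse events. The subject's wish and loss to follow-up complete the list. The subject's wish, medical reasons and adverse events are also reasons for stopping study drug only (Section 5.4.1). No rule says when each use applies.

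**Visit 9 after leaving.** Table 1, footnote 2, sets the end-of-trial visit 7-10 days after the last dose for every randomised subject who received study drug, and adds: "The end-of-trial visit must also be performed if a subject is withdrawn from the trial for any reason". Section 6.5.4 allows a telephone contact and lists among the items recorded "Use of mechanical invasive and non-invasive mechanical ventilation" and adverse events.

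**Counting events.** The main analyses in SAP 6.10.2.3 and 6.10.2.4 end 12 hours after the last dose. The sensitivity analysis of each extends into follow-up. Both first describe follow-up as the time from last dose to Visit 9, and then state that "this analysis will include all data collected from the first treatment administration to the date of study completion or withdrawal". In 6.10.2.3 the event rule repeats the second limit: ventilation or death must be recorded by the date of study completion or withdrawal. In 6.10.2.4, for subjects with neither ventilation nor death at any time after first dose, "the time to need of ventilation will be right censored at the date of withdrawal from study or study completion".

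**The concern.** Study withdrawal and Visit 9 can fall on different days. A subject may leave the trial during the treatment week and still be contacted 7-10 days after the last dose. Ventilation or death in between is then known to the trial, but one of the two stated windows has already closed.

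The two sensitivity analyses exist to recover events that the main analyses cut off 12 hours after the last dose. If they stop at study withdrawal, they fail for subjects whose exit may be related to prognosis. Withdrawal for adverse events or on medical judgement could well be. Protocol Section 3.9 points the same way: it describes the withdrawal criteria as protecting subjects with severe progression, and says that subjects needing ventilation or a different treatment leave the trial. A cut-off related to prognosis can hide a benefit or a harm. In the binary analysis the subject is not censored but scored as a success.

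**Working it through.** **The plan's own figure.** The documents give no figure on this point. Their only design calculation is power for CRP: 75 per arm, difference 25 mg/L, SD 60 mg/L, two-sided 10%. The standard error is 60 × √(2/75) = 9.80, so z = 25/9.80 = 2.55, and 2.55 − 1.645 = 0.907. Power is Φ(0.907) = 81.8% (81.5% with the noncentral t on 148 df), which agrees with the stated approximate 80%. It does not depend on the ventilation follow-up window.

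**One subject under each rule.** Take a subject withdrawn from study drug and from the trial for medical reasons, ventilated two days after the last dose, with the ventilation recorded at Visit 9.

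| Rule | Result |
|---|---|
| 6.10.2.3 main analysis | Not in need of ventilation (12-hour limit) |
| 6.10.2.4 main analysis | Censored 12 hours after withdrawal from treatment |
| 6.10.2.3 sensitivity, window to Visit 9 | Event |
| 6.10.2.3 sensitivity, event rule read literally | Not in need of ventilation |
| 6.10.2.4 sensitivity, event and censoring rules | Event at start of ventilation |
| 6.10.2.4 sensitivity, data-window sentence read literally | Event excluded; subject censored at withdrawal |

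The first two rows do not depend on trial withdrawal, because the 12-hour limit applies to every subject. The conflict lies in the last four rows. It is sharpest in 6.10.2.3, where the event rule itself carries the withdrawal date.

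**What date is study withdrawal?** SAP 6.5 treats the date of early study withdrawal as an alternative to the completion date. Protocol Sections 8.2.1 and 9.3 tie the end of participation to Visit 9. Neither document says which date is recorded when Visit 9 follows trial withdrawal. If it is the Visit 9 date, nothing is excluded.

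**Size, under assumed rates only.** Events outside a window closed at withdrawal = 150 × (proportion leaving the trial early) × (proportion of those ventilated or dying between leaving and Visit 9).

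- 5% leaving, 5% with an event: 150 × 0.05 × 0.05 = 0.4
- 10% leaving, 15% with an event: 150 × 0.10 × 0.15 = 2.25
- 15% leaving, 30% with an event: 150 × 0.15 × 0.30 = 6.75, about 6.8

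**Effect on a comparison, assumed counts.** Suppose 6/75 on C21 and 12/75 on placebo have an event by Visit 9. The odds ratio is (6/69)/(12/63) = 0.46, pooled two-proportion z-test p = 0.13. If 1 C21 event and 3 placebo events fall after trial withdrawal and are ignored, the analysis sees 5 and 9: (5/70)/(9/66) = 0.52, p = 0.26. This removes 4 of 18 events (22%). Both p-values exceed the plan's 10% level, so this example shows attenuation and not a changed conclusion.

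**The case against.** A reader might infer that later ventilation and death in these subjects are simply lost. The documents do not support that as fact, and several counterpoints stand.

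- Both sensitivity analyses also describe follow-up as running to Visit 9. The exclusion is one reading of text that conflicts with itself.
- SAP 6.10.2.4 censors at study withdrawal only subjects with no ventilation and no death at any point after first dose. Its event rule takes ventilation or death from the follow-up period, so an event recorded at Visit 9 would count.
- One might suppose that Visit 9 could be moved to the withdrawal day, so that later events are never seen. No section allows this; Table 1 and Sections 6.1 and 6.5.4 place it 7-10 days after the last dose.
- Section 9.4 says "All AEs should be followed until they are resolved or the subject's participation in the trial ends, whichever comes first", which might suggest that safety data are also cut. Sections 8.2.1 and 9.3 equate the end of participation with Visit 9, and the treatment-emergent definition in SAP 6.11.1 has no end date. A death reported at Visit 9 can reach the safety tables.
- Not everyone leaving the trial is deteriorating. Disallowed drugs include warfarin and strong CYP3A4 inducers (Section 7.8.2), and taking one is not in itself a sign of worsening. Subjects withdrawn from study drug because they need ventilation are already counted as events.
- SAP 6.10.4 makes secondary and supportive analyses descriptive.

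These points limit the scope and the claim of bias. They do not settle what the event rule in 6.10.2.3 means, and two programmers could still classify the same subject differently.

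**Conclusion.** The point holds as an unreconciled conflict over the follow-up window. It is confined to two descriptive sensitivity analyses of secondary endpoints. In SAP 6.10.2.3 the literal event rule turns an event recorded at Visit 9 after trial withdrawal into a success. In 6.10.2.4 only the data-window sentence points that way; the operative event and censoring rules do not.

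The size cannot be derived from the documents. The range of about 0.4 to 6.8 events rests wholly on assumed withdrawal and event rates, and it is zero if the withdrawal date is recorded as the Visit 9 date. That the cut-off is informative is plausible from the listed reasons, but not shown. The correction is still worth making: it uses data the protocol already requires, and it removes an ambiguity that should be settled before unblinding.

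**What to change.** **SAP 6.10.2.3 and 6.10.2.4, sensitivity analyses.** Wherever the window ends at study completion or withdrawal, including the event rule in 6.10.2.3 and the censoring rule in 6.10.2.4, end it at: 'Visit 9, or last contact if Visit 9 was not done'. Add that ventilation or death recorded up to that point counts whether or not the subject was withdrawn from the trial. Subjects with no Visit 9 and no recorded event would still be scored as event-free in the binary analysis; this change does not address that.

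**Protocol.** Reconcile Section 1, Section 3.9, Section 5.4.1 and Section 5.4.2 with Table 1, footnote 2. It should be clear that subjects withdrawn for reasons other than withdrawn consent or loss to follow-up still have Visit 9 at 7-10 days after the last dose. Section 3.9 describes need for ventilation as withdrawal from the trial, while Sections 1 and 5.4.1 describe it as withdrawal from study drug; the sponsor should make these agree. The list of withdrawal reasons need not be rewritten.

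**Cost.** The SAP change is a few phrases, made before unblinding. It adds no subjects, visits or procedures, since Visit 9 is already required and may be by telephone. Any protocol change judged substantial needs regulatory and ethics approval (Section 10.1), with sites in the UK and India, but the SAP correction need not wait for it.

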2 FLOW CHARTS

Table 1 Flow Chart for Trial Procedures

	Screening		Treatment Period			With- drawal ¹⁾	End-of- Trial ²⁾			
Visit Number	Visit 1	Visit 2	Visit 3	Visit 4	Visit 5	Visit 6	Visit 7	Visit 8	-	Visit 9
Visit window (days allowed from previous visit)		1-3	1	1	1	1	1	1	-	7-10 ²⁾
Eligibility / General										
Informed consent	X									
Check eligibility criteria	X	x ³⁾								
Demographics	X									
Medical history	X									
Randomisation		X								
Supplemental O ₂	X	X	X	X	X	X	X	X		X
Previous/concomitant medication	x	X	X	x	x	x	x	x	х	x
Check of withdrawal criteria		X	X	x	x	x	x	x		
Clinical Safety										
Physical examination ⁴⁾	x ⁴⁾	X	X	X	X	X	X	X		
Body weight	X									
Height	X									
Body temperature	X	X	X	X	X	X	X	X		
Vital signs	X	X	X	X	X	X	X	X		
12-lead ECG ⁵⁾	X									
Adverse events	X	X	X	X	X	X	X	X	X	х
IMP										
IMP administration ⁶⁾		X	X	x	X	X	X	X		
Check of fasting criteria		X	X	X	X	X	X	X		
Drug accountability								X	X	

- 1) Additional withdrawal assessments must be performed at Visit 2-8 if the subject is prematurely withdrawn from IMP (see Section 6.5.3)
- 2) An end-of-trial visit for all randomised subjects who received IMP must be performed 7-10 days after the last dose of IMP. The end-of-trial visit must also be performed if a subject is withdrawn from the trial for any reason.
- 3) Re-evaluation of in-/exclusion criteria including evaluation of ECG and laboratory results from Visit 1
- 4) A complete physical examination will be performed at Visit 1. At Visits 2-8, only a short physical examination will be performed (see Section 8.2.4)
- 5) All ECGs will be reviewed locally
- 6) IMP is administered twice daily (see Section 7.4)

Vicore Pharma AB Version: 2.0 Trial ID: VP-C21-006 Date: 14-Aug-2020

Table 2 Flow Chart for Laboratory Assessments

Visit	Screening		Treatment Period				With- drawal ¹⁾	End-of- Trial ²⁾		
Visit Number	Visit 1	Visit 2	Visit 3	Visit 4	Visit 5	Visit 6	Visit 7	Visit 8	-	Visit 9
Visit window (days allowed from previous visit)		1-3	1	1	1	1	1	1	-	7-10
Laboratory Sampling										
HCV Ab	X									
HBsAg	X									
HIV 1+2 Ag/Ab	X									
Biochemistry ⁷⁾	X	х	x	X	X	X	X	X		
Haematology ⁸⁾	X	X	X	X	X	X	X	X		
CRP	X	X	X	X	X	X	X	X	X	
IL-6		X	X	X	X	X	X	X		
IL-10		X	X	X	X	X	X	X		
TNF		X	X	X	X	X	X	X		
CA125		X	X	Х	X	X	X	X		
Ferritin		X	X	X	X	X	X	X		
Urinalysis 9)	Х	Х	X	X	X	X	X	X		
Biomarkers		X						X	X	
Pregnancy testing 10) 11)	X							X	X	

- 7) Haematology: haemoglobin, haematocrit (erythrocyte volume fraction), platelet count (thrombocyte particle concentration [TPC]), leucocyte count, mean corpuscular volume (MCV), white blood cells with differential count (see Section 8.2.7)
- 8) Biochemistry: albumin, alanine transferase (ALT), aspartate aminotransferase (AST), alkaline phosphatase (ALP), bilirubin, blood urea nitrogen (BUN), calcium, creatinine, glucose, potassium, sodium (see Section 8.2.7)
- Urinalysis: dipstick for bilirubin, glucose, ketones, protein, specific gravity, urobilinogen, and pH (see Section 8.2.7)
- 10) Only applicable for female subjects of childbearing potential, as defined in Section 5.3.1.
- 11) Urine dipstick is performed if positive for pregnancy this is to be followed up by a pregnancy blood test

Vicore Pharma AB Version: 2.0 Trial ID: VP-C21-006 Date: 14-Aug-2020

3 BACKGROUND AND RATIONALE

3.1 Indication Coronavirus Disease (COVID-19)

Coronavirus disease (COVID-19) is a viral infection caused by the newly emergent coronavirus SARS-CoV-2 (World Health Organization [WHO] In January 2020, SARS-CoV-2 was identified as the causative agent of an outbreak of viral pneumonia centered around Wuhan, Hubei, China, where the first cases were reported in December 2019 (Wu et al., 2020; Zhou et al., 2020; Lu et al., 2020). The virus caused a widespread outbreak of infection throughout China. It rapidly expanded globally and by March 12, 2020, COVID-19 was announced a pandemic by the World Health Organization (WHO).

SARS-CoV-2 is currently thought to originate from a bat host (Zhou et al., 2020; Lu et al., 2020), probably with an intermediate animal host passing the virus from bats to humans (Lake et al., 2020). Human-to-human transmission is now well established and the transmission occurs via the respiratory route or via contact with infected secretions. The basic reproduction number, R₀ (the expected number of secondary cases produced by a single [typical] infection in a completely susceptible population), is currently estimated by the WHO as 1.4-2.5 (Phan et al., 2020). Based on 425 cases identified in early January 2020 in Wuhan, the mean incubation period was estimated to be 5.2 days (Li et al., 2020).

COVID-19 infection can cause mild to severe respiratory illness, and symptoms can include fever, cough, and shortness of breath (WHO 2020). As of April 1., 2020, the WHO has reported 823,626 confirmed cases of COVID-19 and 40,598 deaths globally. At present, the European region is the region that is most severely affected with 464,212 confirmed cases of COVID-19 and 30,089 deaths.

Most reported cases of COVID-19 illness are mild, but severe disease is not uncommon. Currently, data are limited but early studies from China have shown that severity was related to the burden of comorbidities including diabetes, hypertension, and cardiovascular disease as well as to increasing age (WHO 2020; Huang et al., 2020). Dysregulation of the renin-angiotensin system (RAS) cascade is present in each of these comorbidities and could increase the likelihood or severity of SARS-CoV-2 infection (Hanff et al., 2020).

Estimates of case fatality ratio (CFR) of COVID-19 are uncertain. In an early trial including 1,975 confirmed cases in China, the CFR was 2.8% (Wang et al, 2020). In a new trial including 70,117 cases in China, a CFR of 3.67% was estimated (Verity et al., 2020). In the same trial, the authors made a best estimate of the CFR in China of 1.38% after adjusting for demography and underascertainment and found substantially higher CFRs in age groups above 60 years than below 60 years.

Initial symptoms are not necessarily predictive of disease severity. Several very recent publications have shown that CRP is an indicator of COVID-19 progression that predicts severe disease (e.g. Li et al., 2020; Tan et al., 2020; Wang et al, 2020) and mortality (Ruan et al., 2020).

Vicore Pharma AB Version: 2.0 Trial ID: VP-C21-006 Date: 14-Aug-2020

